Subjects will receive a first intravenous (i.v.) bolus of 10 mg ALX-0081 or placebo via push injection within 6h, but not later than 15 minutes prior to the initiation of PE on study (which can either be the very first PE session, if the subject was randomised prior to the initiation of PE, or the second PE session, if the subject was randomised after one, single PE session; see section 4.2). This first PE on study is followed by subcutaneous (s.c.) administration of 10 mg study drug.

Subsequently daily s.c. administrations of 10 mg ALX-0081 (Table 1) or placebo will follow each PE session for the duration of PE (including tapering and PE given for exacerbations) and once daily for 30 days following the very last PE (including tapering) (Table 1). The maximum total daily dose of study drug is 10 mg when administered in conjunction with PE (20 mg only in case twice daily PE sessions are needed) and 10 mg when in the period following the very last PE (including tapering). Study drug administration will continue in case of re-initiation of PE for an exacerbation of TTP, with a maximum total treatment duration limited to 90 days after first administration of study drug.

At \leq 30 days after the last day of study drug administration, subjects will be assessed for the primary and secondary endpoints of the study, and will be followed for a maximum of 1 year for relapses and other tertiary [REDACTED] endpoints.

Laboratory parameters for inclusion, study conduct, safety assessments and assessments of response/relapse, re-treatment and study medication dose modification will be assessed at each local site laboratory.

An independent Data Safety Monitoring Board (DSMB) will monitor accruing safety data during the study (SAEs on an ongoing basis and 'early safety look' when 16 subjects, 8 ALX-0081 treated and 8 placebo-treated, have completed treatment with study drug) and will make recommendations on continuation of the study as appropriate. An interim analysis for safety with formal stopping rules is foreseen when 28 of the ALX-0081 treated subjects have been treated, and will make a recommendation on study continuation or discontinuation. No review of efficacy data by the DSMB is foreseen.

Planned Sample Size

It is anticipated to include 110 patients with acquired TTP.

Study Period

- 30 months recruitment period is anticipated.

- 12 months of follow-up after last administration of study drug (until last subject completes the 12-month follow-up visit).

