7.2 Treatment and Dosing Regimen for Study Drug

The study drug will be administered as adjunctive treatment at specific times relative to the PE procedures. The study drug consists of 10 mg of ALX-0081 or placebo, once or twice daily as explained below (Table 8).

Subjects will receive a first i.v. bolus of 10 mg ALX-0081 or placebo via push injection within 6h, but not later than 15 min prior to the initiation of PE on study (i.e., the very first PE session, if the subject was randomised prior to the initiation of PE, or the second PE session, if the subject was randomised after one, single PE session; see section 4.2). This first PE on study is followed by s.c. administration of 10 mg study drug within 30 minutes after the end of the PE procedure.

During the complete PE treatment period (including tapering and PE given for exacerbations), study drug will be administered daily via s.c. injections.

- If 1 PE per day is scheduled, 10 mg of study drug will be administered within 30 minutes after the end of the PE procedure.
- If 2 PEs per day are scheduled, 10 mg of study drug will be administered within 30 minutes after the end of each PE procedure. The maximum total daily dose of study drug is hence 20 mg.
- If less than 1 PE per day is scheduled (i.e. during a tapering regimen), 10 mg of study drug will be administered daily. On days with a PE, study drug administration should be within 30 minutes after the end of the PE procedure; on days without PE, study drug administration should be 24 h (\pm 1 h) after previous administration

Daily s.c. study drug administration of 10 mg will continue for 30 days after the very last PE (including tapering).

Maximum treatment duration with study drug will be limited to 90 days after first administration of study drug.

In case of exacerbation of TTP (after \geq 1 day but \leq 30 days after the last daily PE), standard treatment (PE) should be re-initiated and daily s.c. administration of study drug continued.^a The “study drug post-PE” period (for 30 days after the very last PE, see Figure 5 further below) will re-commence once PE is again stopped. Maximum treatment duration with study drug will be limited to 90 days after first administration of study drug.

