 - 4 samples: prior to study drug and at 1-6 h, 6-12 h, 18-24 h post-study drug, but prior to next administration of study drug or before next PE (in case of tapering)
 - Subsequent time interval until the last day of study drug administration:
 - 2 samples once-weekly: prior to study drug administration (but after PE, in case of tapering) and 4-8 h post-study drug. Of note, for each day that a follow-up at the investigational site is planned, the

administration of 10 mg study drug will be performed during the follow-up visit in the investigational site.

- Blood samples for ADA (central lab) need to be taken on day 14, and then weekly until the last day of study drug administration.
- Blood sampling for ADAMTS13 and anti-ADAMTS13 antibody titre (central laboratory). This blood sampling needs to be performed on the first day after the daily PE period and 1 week post last day of PE (including tapering) and at 3 weeks post last day of PE (including tapering); the 1 week and 3 weeks after the very last PE (including tapering) sampling may be done at the weekly visit, even if not exactly 1 or 3 weeks.
- Retrieval of 30 mL from the first bag of pathological spent plasma resulting from the first PE procedure on study. This will be divided in aliquots of 5 mL each for storage at -70°C. The retrieved spent plasma, obtained from the first plasma exchange on study, and the first spent bag will be used for following purposes.
 - As matrix for development and validation of ADA, biomarker assays that will be used in TITAN trial.
 - For further characterisation of possible immunogenicity findings.
 - For additional measurement of vWF and ALX-0081 concentrations under R&D conditions and subsequent PK/PD modelling to assess extent of removal of these components upon plasma exchange.
- Recuperate nurse sheet and/or AE diary at each post discharge visit.

An overview of assessments performed during the treatment phase of this trial is provided in Table 11.

Assessments scheduled in case of TTP exacerbation

In case of TTP exacerbation, defined as recurrent thrombocytopenia following a response and requiring a re-initiation of daily PE treatment after ≥ 1 day but ≤ 30 days after the last daily PE, the assessments scheduled for “Day 1 after last daily PE” are not performed after completion of the exacerbation treatment, instead, the “post-daily PE (including tapering)” assessments are continued. A dedicated schedule of assessments is provided in Table 12.

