### 6.3.2 Secondary Efficacy Variables

#### *Secondary Endpoints*

All endpoints achieved within 30 day period after end of study drug treatment:

- Number and percentage of subjects with complete remission (defined as confirmed platelet response and absence of exacerbation)
- Number and percentage of (subjects with) exacerbations of TTP (defined as recurrent thrombocytopenia following a confirmed platelet response and requiring a re-initiation of daily PE treatment after  $\geq 1$  day but  $\leq 30$  days after the last daily PE) and time to first exacerbation of TTP
- Number of daily PE sessions, number of total volume of plasma administered and number of days of daily PE
- Total mortality within the PE treatment period and within the subsequent study drug treatment period (including tapering)
- Number and percentage of subjects relapsing of TTP (defined as *de novo* event of TTP that occurs later than 30 days after the last daily PE)
- Number and percentage of subjects with platelets  $\geq 150,000/\mu$ L at day 30 of study drug administration (last treatment day visit) and one month follow-up time point
- Resolution or improvement (improvement of  $\geq 1$  grade in the CTCAE v4.0 scale) of TTP-related signs and symptoms as captured on physical examination and as adverse events, at complete remission and at end of the study drug treatment period (including tapering) (by number of unique subjects and by total number of AEs)
- Incidence of PE treatment-related AEs, such as, but not restricted to: haemorrhage from catheter insertion, sepsis, catheter thrombosis, pneumothorax, fluid overload, hypoxia, hypotension, anaphylactoid reactions and TRALI

---

This study has been statistically powered for the primary endpoint. No adjustment for multiplicity has been applied to the exploratory analysis for the secondary variables. All analysis will be performed on the ITT and PP populations and any p-values presented for secondary efficacy variables are purely exploratory (e.g. comparison of the number and percent of subjects with complete remission, exacerbations, relapse and daily PEs).

The number and percentage of subjects with complete remission at one month post first administration of study treatment, along with the exact binomial CI of the percentage will be presented by treatment group, overall and by ADAMTS13 activity  $< 5\%$  vs.  $\geq 5\%$  at baseline.

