**Table 3 Schedule of assessments during treatment phase in case of exacerbation**

Assessment/ Activity	Daily PE treatment phase	Post daily PE (including PE tapering)
Treatment with study drug	Once daily or twice daily (only if twice daily PE) a	once daily $\pm$ 2 hours
Concomitant medication recording other than PE-related treatment	all	weekly $\pm$ 2 days
PE details b	all	NA or all in case of tapering
Subject review/clinical assessment, including vital signs	daily	weekly $\pm$ 2 days
AE recording	daily (all)	weekly $\pm$ 2 days (all)
Glasgow Coma Score	weekly if abnormal at screening	weekly if abnormal at screening and if subject hospitalised
Neurocognitive battery	no	no
Modified ITP bleeding score	daily	weekly $\pm$ 2 days
Clinically relevant bleeding	daily	weekly $\pm$ 2 days
12-lead ECG	daily if abnormal at baseline. on day 1 and day 4, 4-6 h post-study drug	weekly $\pm$ 2 days
Blood chemistry (local lab)	daily pre-PE	weekly $\pm$ 2 days
Haematology (local lab)	daily pre-PE	weekly $\pm$ 2 days
Coagulation variables (local lab)	Mon, Wed, Fridays	weekly $\pm$ 2 days
Cardiac marker (TnT or TnI) (local lab)	daily pre-PE if value > ULN in baseline or at day 1	weekly $\pm$ 2 days if value > ULN in baseline or at day 1
BNP or NT proBNP (local lab)	Mon, Wed, Fridays pre-PE if value > ULN in baseline or at day 1	weekly $\pm$ 2 days if value > ULN in baseline or at day 1
Brain damage markers (NSE, S $\beta$ 100) (central lab)	Mon, Wed, Fridays pre-PE	weekly $\pm$ 2 days

Assessment/ Activity	Daily PE treatment phase	Post daily PE (including PE tapering)
PK (central lab)	No	2 samples weekly: 
 
• prior to study drug, but after PE (in case of tapering)
 
• 4-8 h post-study drug
 

RICO (central lab)	daily pre-PE	weekly $\pm$ 2 days (pre-PE in case of tapering)
vWF (central lab)	No	coupled to PK above
FVIII chromogene (central lab)	No	coupled to PK above
ADA (central lab)	No	weekly until the last day of study drug administration
ADAMTS13 and anti-ADAMTS13 antibody titre (central lab)	No	1 week and 3 weeks after the very last PE, including tapering e
Spent plasma retrieval	No	no
Recuperate nurse sheet and/or AE diary	NA	Post-hospital discharge: weekly $\pm$ 2 days d

a Once or twice daily as detailed in the Treatment and Dosing Regimen for study drug Section 7.2 of the protocol.

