If study drug administration is not stopped when clinically relevant bleeding occurred	Monitoring check of CRF and Check in DB for start date CRB = stop date study drug (note that study drug is reported on daily basis, in fact the date should be missing in 'EX'). Also the bleeding is to be reported as AE with action taken regarding trial med = dose interrupted	██████████ ██████  ██████████ ██████	Review of listings or edit checks	Bleeding occurred but drug not interrupted	Investigator mistake
If study drug is restarted when vWF:Ag < 50% and FVIII not normalised	Monitoring check of CRF and Check in DB for start date of study drug ≥ date of local lab vWF:Ag > 50% and FVIII value in normal range	██████████ ██████  ██████████ ██████	Review of CTMS entries and listings Review of listings or edit checks	Drug restarted but vWF:Ag and FVIII levels not recovered yet	Investigator mistake
Study drug administration					
During daily PE treatment period					
Excursion of time window of sc administration after each daily PE to > 30 min post PE	Also dosing pre-PE is considered as major violation	██████████	Review of listings or edit	Excursion of dosing time	Treatment non compliance

Major PD categories	Remarks	Source	How to assess?	DVTERM	DVDECOD
			checks	window in daily PE period	
If $\geq 1$ dose(s) are missed during daily PE treatment period		██████████	Review of listings or edit checks	Missing dose during x days in daily PE period	Treatment non compliance
During tapered PE (as applicable) and the 30 days post daily PE treatment period					
If study drug was administered on $< 75\%$ of treatment days	If $\geq 25\%$ of doses (e.g. 0.25 x 30 days = 7.5 $\Rightarrow$ 8 days) were not administered	██████████	Review of listings or checks	Subject not dosed on x days out of y days during post daily PE period	Treatment non compliance
If $\geq 2$ consecutive doses were not administered	If PE is given (PE tapering): Drug should be given within 6 hours after PE; otherwise, consider as missing dose.	██████████	Review of listings or checks	Subject not dosed on x consecutive days during post daily PE period	Treatment non compliance
Applies to whole drug treatment period (during and after PE period)					
Randomised, no treatment administered		██████████	Review of listings or check	Randomised, no treatment	Investigator mistake

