One or more incorrect (i.e. not as per randomised treatment assignment) treatment administrations		██████████	Review of CTMS entries Review of listings	Incorrect treatment administered (placebo/verum instead of verum/placebo)	Treatment non compliance
Administered more than protocol prescribed dose (overdose): if more than 1 dose and no or 1 PE on that day if more than 2 doses and not 2 PEs on that day		██████████	Review of CTMS entries	Subject overdosed (x doses instead of y)	Treatment non compliance
One PE prior to randomisation					

Major PD categories	Remarks	Source	How to assess?	DVTERM	DVDECOD
Prior to protocol amendment 12 any PE prior to randomisation is considered a major protocol deviation	Ablynx maintain a listing of which protocol version each subject is enrolled under. This will need to be used in collaboration with the PE and randomisation dates from the database in order to identify violating subjects.	██████████ ██████████	Review of listings or check	X PE done before randomisation	Eligibility criteria not met
Starting from protocol amendment 12 first PE ended more than 24h prior to randomisation is considered a major protocol deviation.	As above	██████████ ██████████	Review of listings or check	PE done x hours before randomisation	Eligibility criteria not met
Starting from protocol amendment 12 more than one PE prior to randomisation is a major protocol deviation	As above	██████████ ██████████	Review of listings or check	X PE done before randomisation	Eligibility criteria not met
Other					
Disallowed concomitant therapy taken: only one disallowed = desmopressin	Any concomitant medication with HTC code "H01BA" (coded term "VASOPRESSIN AND ANALOGUES").	██████████	Review of listings	Disallowed medication taken (name of drug, start date – stop date)	Excluded concomitant medication
Subject becomes pregnant but is not withdrawn from the trial		██████████	Review of listings	Subject pregnant but not withdrawn	Subject not withdrawn as per protocol
Subject is lost to follow up but is not withdrawn from the trial	If a subject is lost to follow up, they should be in the database as discontinued otherwise a query should fire, so at the end of the study there should be no subjects lost to follow-up who were not withdrawn.			Subject lost to follow up but not withdrawn	Subject not withdrawn as per protocol

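### A scheduled dose taken before plasma exchange is restarted for an exacerbation can make a compliant subject a major deviator, so PP loses subjects because they had the endpoint

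*SAP*

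**What the plan says.** SAP Appendix II sorts study-drug deviations into three blocks.

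- **Daily PE treatment period.** The timing row reads "Excursion of time window of sc administration after each daily PE to > 30 min post PE", with the remark "Also dosing pre-PE is considered as major violation". One missed dose in this period is also major.
- **Tapered PE and the 30 days after daily PE.** Major deviations are dosing on fewer than 75% of days, or two or more consecutive missed doses.
- **Whole treatment period.** The overdose row includes "if more than 1 dose and no or 1 PE on that day".

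SAP section 6.2.2 removes major deviators from PP. SAP section 6.3.2 lists exacerbation and complete remission among the secondary endpoints and states: "All analysis will be performed on the ITT and PP populations".

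For an exacerbation, Protocol 7.2 says that "standard treatment (PE) should be re-initiated and daily s.c. administration of study drug continued". The same section calls for a dose within 30 minutes after the end of a once-daily PE, and it counts PE for exacerbations in the PE treatment period. The protocol synopsis says "The maximum total daily dose of study drug is 10 mg when administered in conjunction with PE", with a higher maximum only for twice-daily PE. Neither document says how a dose already given on the restart day is to be treated or classified.

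**The concern.** An exacerbation arises after daily PE has stopped, when the subject is on one scheduled dose a day. If PE is restarted later on a day when that dose has been given, the dose came before a PE through no error by the site. Appendix II has no exemption for this day.

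The sequence is plausible. In the post-daily-PE phase haematology is scheduled weekly, and Protocol 8.1.2 says that on site-visit days "administration of 10 mg study drug will be performed during the follow-up visit in the investigational site". The visit that can reveal a falling platelet count is therefore also a dosing visit.

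What is at stake is a PP exclusion triggered by the outcome being analysed. A subject without an exacerbation cannot be excluded in this way. PP would then be a poor sensitivity check on exacerbation and on complete remission, which requires the absence of exacerbation.

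**Working it through.** **Step 1: do the daily-PE lines apply on the restart day?**

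For:
- SAP section 3 defines exacerbation by re-initiation of daily PE.
- Protocol 7.2 includes PE for exacerbations in the PE treatment period.
- SAP Table 3, titled "Schedule of assessments during treatment phase in case of exacerbation", has a column for a daily PE treatment phase.
- SAP section 4 places tapering outside the daily PE period but does not do the same for exacerbation PE.

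Against:
- Appendix II never says that the block reopens.
- The exposure definitions in SAP section 3 can be read as one daily-PE period followed by everything else.
- Table 3 is an assessment schedule, not a deviation rule.

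The first reading is better supported, but the text does not settle it.

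**Step 2: classify the restart day** (one scheduled s.c. dose already given, one PE, literal wording).

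| Further dose after the PE | Daily-PE lines apply again | Daily-PE block is the first course only |
|---|---|---|
| None | Major: pre-PE line | Not flagged by this day alone |
| One | Major: pre-PE and overdose lines | Major: overdose line |

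Under the first reading a second PE that day does not remove the pre-PE flag, because the earlier dose cannot be undone.

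**Step 3: effect on PP rates.** The plan gives no figure to reproduce, and all rates here are assumed. Let r be the true exacerbation rate in an arm and f the share of its exacerbators flagged on the restart day. Ignoring other PP exclusions, the flagged fraction rf leaves both numerator and denominator:

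PP rate = r(1 − f) / (1 − rf)

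Take r = 0.25 for placebo and 0.10 for ALX-0081, with f equal in both arms. At f = 0.5, placebo is 0.125/0.875 = 14.3% and ALX-0081 is 0.05/0.95 = 5.3%.

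| f | Placebo | ALX-0081 | Difference (points) | Risk ratio |
|---|---|---|---|---|
| 0 | 25.0% | 10.0% | 15.0 | 2.50 |
| 0.3 | 18.9% | 7.2% | 11.7 | 2.62 |
| 0.5 | 14.3% | 5.3% | 9.0 | 2.71 |
| 0.7 | 9.1% | 3.2% | 5.9 | 2.82 |

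With 55 subjects per arm (110 randomised 1:1) and f = 0.5, this rule removes about 55 × 0.25 × 0.5 = 6.9 placebo and 55 × 0.10 × 0.5 = 2.8 ALX-0081 subjects.

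**Step 4: complete remission.** None of the removed subjects is in complete remission. A true remission rate m therefore becomes m/(1 − rf), which is higher. If every subject had a confirmed platelet response (assumed), m = 1 − r. At f = 0.5 the rates rise from 75% to 0.75/0.875 = 85.7% on placebo, and from 90% to 0.90/0.95 = 94.7% on ALX-0081.

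**Step 5: unequal f.** With f = 0.3 on placebo and 0.7 on ALX-0081, the difference is 18.9 − 3.2 = 15.7 points, slightly above the true 15. With the shares reversed it is 9.1 − 7.2 = 1.9 points. The direction of the effect on the arm comparison is therefore not fixed.

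**The case against.** A reader might infer that no conduct on the restart day avoids a major deviation. The documents do not support that. If the daily-PE block means only the first course, a subject given no second dose is not flagged: the post-daily-PE lines need two consecutive missed doses or fewer than 75% of days dosed. This part of the objection stands.

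The overdose line cannot always be read literally. On the first treatment day every compliant subject receives an i.v. dose before PE and an s.c. dose after it, so a literal reading would flag nearly everyone with one PE that day. The line has to be read with its own description, a dose above what the protocol prescribes. This stands too, but it does not clear the restart day. Protocol 7.2 calls for a dose after the PE and the synopsis caps the daily total, so whether a post-PE dose exceeds the prescription is unresolved.

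Deviations are assessed by review of listings, edit checks or trial-management entries, exclusions are fixed before database lock without regard to study drug assignment, and SAP section 6.2.2 gives the sponsor decisions on exclusion. That could settle individual cases. However, the same section says major deviators leave PP, and case-by-case rulings on subjects known to have had the endpoint are no substitute for a written rule.

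The rates are assumed, and exacerbators may leave PP anyway through other daily-PE lines, so the added loss from this one day is unknown. This stands.

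**Conclusion.** The concern holds as a gap in the PP classification. On the better-supported reading, a dose that was correct when given makes an exacerbating subject a major deviator. On the narrower reading this happens only when a post-PE dose follows, and then through the literal overdose line. Either way, some compliant subjects would leave PP as a consequence of the endpoint, lowering PP exacerbation rates and raising PP complete-remission rates.

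A reader might go further and say that the rule pulls the PP treatment effect towards no difference. That is true only of the absolute difference, and only if the pre-dosed share is similar in both arms. In the illustration the difference falls from 15.0 to between 11.7 and 5.9 points, while the risk ratio moves away from 1, from 2.50 to between 2.62 and 2.82.

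The true size cannot be derived: the documents give neither exacerbation rates nor the times of day of doses and PE restarts. Only supportive PP analyses are affected. ITT is the primary efficacy population, and the SAP calls the secondary p-values exploratory. The point merits correction because the repair is cheap, not because it threatens the main result.

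**What to change.** Before PP exclusions are settled, add to SAP Appendix II:

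1. The daily-PE lines apply to PE re-initiated for an exacerbation.
2. A scheduled dose given earlier on the restart day, before PE was restarted, does not trigger the pre-PE line and is not counted toward the overdose line.
3. For such a subject, the presence or absence of a post-PE dose that day is not a time-window, missed-dose or overdose deviation.
4. All other dosing errors that day still count.

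The cost is a short addition to Appendix II and one condition in the deviation program. The downside is that a true error involving that one post-PE dose would not count for PP. This is narrower than exempting the whole day, which would also hide unrelated errors.

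Separately, the sponsor should reconcile Protocol 7.2 (a dose after the PE) with the synopsis (the daily maximum) for the restart day. No dosing rule is proposed here; the addition to Appendix II concerns only how the analysis classifies subjects.

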### **6.2.2 Protocol Deviations**

A protocol deviation is defined as failure to fully comply with the study protocol. The deviation can be classified further as:

- 
- Minor Protocol Deviation – does not have an impact on the subject’s rights, safety or wellbeing, or the completeness, accuracy and reliability of the study data
  - Major Protocol Deviation – may affect the subject’s rights, safety or well being and/or the completeness accuracy and reliability of the study data

The sponsor will make any decisions regarding whether any subjects or any individual parameters pertaining to a subject will be excluded from the safety and efficacy evaluations when the protocol deviation is considered to have a negative impact on scientific aspects and interpretation of the study results.

Major protocol deviations will be excluded from the PP population.

All major protocol deviations will be listed. Major protocol deviations will be summarised by treatment group and overall for the ITT population.

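### Three SAP rules misfire as written, affecting only the temperature summaries and the per-protocol analyses: the Fahrenheit conversion is inverted, the overdose sub-lines catch a first day dosed as scheduled, and the PP definition gains an undeclared completion condition.

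*SAP*

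**What the plan says.** **Temperature.** SAP 3 obtains degrees Celsius by taking the Fahrenheit value, multiplying by 9, dividing by 5 and adding 32. SAP 6.4.3 notes that the CRF allows a choice of units, refers to Section 3 for the conversion, and summarises both absolute values and change from baseline in Celsius.

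**Overdose.** The Appendix II row opens with "Administered more than protocol prescribed dose (overdose" and has two sub-lines. The first reads "if more than 1 dose and no or 1 PE on that day"; the second covers more than two doses when the number of plasma exchanges (PEs) that day is not two. The row stands under the heading "Applies to whole drug treatment period (during and after PE period". Its deviation term is "Subject overdosed (x doses instead of y", and its only stated method of assessment is review of CTMS entries. Protocol 7.2 says "Subjects will receive a first i.v. bolus of 10 mg ALX-0081 or placebo via push injection" before the first PE on study, followed by 10 mg s.c. after that same PE; SAP 1.2 and 6.2.5 repeat this.

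**PP population.** Protocol 10.1 takes randomised subjects and removes major violators. SAP 6.2.2 says the same: "Major protocol deviations will be excluded from the PP population". SAP 2 requires no major deviation and, in addition, satisfactory completion of the study. SAP 6.1.5 lists three changes from the protocol, and this is not one of them.

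**The concern.** The temperature rule gives a wrong value for every Fahrenheit entry.

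The overdose row contradicts its own lead-in. A first day dosed as scheduled is not more than the protocol prescribes, and its deviation term would read two doses instead of two. It also conflicts with SAP 6.2.2: "A protocol deviation is defined as failure to fully comply with the study protocol". At the same time, the row misses real excess dosing on 2-PE days.

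The completion clause makes PP membership depend on survival and retention after randomisation.

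PP is used for the second Kaplan-Meier analysis of the primary endpoint, is the first listed sensitivity analysis, and is used for the secondary endpoints. SAP 2 says that PP exclusions follow the Appendix II criteria. Membership should therefore follow from rules that do not have to be waived for compliant subjects.

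**Working it through.** **1. Temperature.** The SAP rule is C = F × 9/5 + 32; the conversion needed is C = (F − 32) × 5/9.

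| °F | SAP rule | Correct °C | Error |
|---|---|---|---|
| 95.0 | 203.0 | 35.0 | 168.0 |
| 98.6 | 209.48 | 37.0 | 172.48 |
| 104.0 | 219.2 | 40.0 | 179.2 |

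Putting 37 into the SAP formula returns 98.6, which shows that it runs the wrong way. When both readings are in °F, a change is multiplied by 9/5 instead of 5/9: (9/5)/(5/9) = 3.24. A true change of −1.0 °C is reported as −3.24. The share of Fahrenheit records is not given. Near 98.6 °F, each 1% of such records raises a mean by about 0.01 × 172.48 = 1.7.

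**2. Overdose sub-lines.** With D doses and P exchanges on a day, sub-line 1 fires if D > 1 and P ≤ 1; sub-line 2 fires if D > 2 and P ≠ 2.

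| Day | D | P | Sub-line 1 | Sub-line 2 |
|---|---|---|---|---|
| First day as scheduled, one PE, same day | 2 | 1 | **fires** | no |
| Bolus only, PE after midnight | 1 | 0 | no | no |
| Later day, one PE | 1 | 1 | no | no |
| Tapering day without PE | 1 | 0 | no | no |
| Two PEs, a dose after each | 2 | 2 | no | no |
| Two PEs, once-daily dose | 1 | 2 | no | no |
| Two PEs, three doses | 3 | 2 | no | no |
| Two PEs, four doses | 4 | 2 | no | no |

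The only scheduled day in the table that is flagged is the first. With P of 0 or 1, D > 2 already implies D > 1, so sub-line 2 adds nothing. With P = 2, neither sub-line can fire, whatever D is. Sub-line 2 adds cases only at three or more PEs, a frequency that protocol Table 8 does not list. The first-day result also depends on what a day is, because the bolus may precede the PE by up to 6 hours.

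The prescribed dose itself is not stated consistently. The protocol synopsis and SAP 1.2 put the daily maximum at 10 mg with PE, and 20 mg only with twice-daily PE. The scheduled first day with one PE totals 10 + 10 = 20 mg. For 2-PE days, the text of protocol 7.2 gives study drug after each PE without distinguishing the arms, whereas Table 8 keeps placebo subjects on once-daily dosing.

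**3. Completion clause.** SAP 3 defines study completion as the treatment phase plus 30 days after the last dose. With treatment capped at 90 days, this can run to day 90 + 30 = 120. The primary endpoint window is 30 days from first dose, and the 15% loss assumed in SAP 6.1.4 refers to those 30 days, so it says nothing about loss up to day 120.

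An illustration: platelets recover on day 5 and are confirmed on day 7, which is also the last PE. Study drug then runs to about day 7 + 30 = 37, and completion falls at about day 37 + 30 = 67. If this subject withdraws on day 60, the primary outcome is fully known, but the subject leaves PP.

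SAP Table 1, labelled for ITT and PP, censors at day x a subject who has left the trial without an event (case 4). Such a subject cannot have completed the study, so the clause would leave case 4 empty in PP.

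**The case against.** The strongest reply concerns the overdose row. It is assessed by reading CTMS entries, while several neighbouring rows name listings or edit checks. Its lead-in limits it to more than the prescribed dose, and the sub-lines resemble the s.c. dosing grid of Table 8, where the bolus stands apart. Reviewers may well waive the first day. This stands. A reader might infer that most correctly dosed subjects would drop out of PP, but the documents do not support that: no programmed count is specified, and the sponsor decides on exclusions under SAP 6.2.2. What remains is a written criterion that contradicts itself and is blind on 2-PE days.

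A reader might also take the s.c. timing row, "Also dosing pre-PE is considered as major violation", to outlaw the bolus. The row concerns s.c. administration, so in context it does not.

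On completion, a reader might set the protocol's definition of a completed subject (5.4.1, all follow-up visits) against the SAP and infer that PP could not be fixed at the one-month lock. That does not hold. SAP 3 defines study completion and follow-up completion separately, and the PP wording matches the first. Only the qualifier, satisfactory, is left undefined.

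It is fair to say that the protocol leaves analysis detail to the SAP, and that listing the clause in 6.1.5 would cure the non-disclosure. It would not cure the selection on retention. The Table 1 argument is supporting only: case 7 (not dosed) is also impossible in PP, because Appendix II makes it a major deviation, so the table's label is loose.

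Finally, temperature is a descriptive safety summary, and absolute values above 200 would probably be noticed at output review. An inflated change from baseline is easier to miss.

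**Conclusion.** All three defects hold on the text, within a limited scope.

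- **Temperature:** an outright error in Fahrenheit entries, about +172 at normal body temperature and a factor of 3.24 on changes. The effect on the tables depends on the unknown share of Fahrenheit records.
- **Overdose:** a criterion that flags scheduled dosing and misses three or more doses on a 2-PE day. It rests on a literal reading, with the bolus and the s.c. dose on the same day. The number of subjects affected is unknown and may be none, so no loss of PP power is claimed.
- **Completion:** an undeclared narrowing of PP that selects on post-randomisation retention. The number lost cannot be derived from the documents.

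The ITT log-rank test and the sample size of 110 are not affected. The corrections are worth making before lock because each rule gives a wrong or unintended result if followed as written.

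**What to change.** 1. **SAP 3:** replace the temperature rule with C = (F − 32) × 5/9.
2. **Dosing passages, then Appendix II:** first reconcile the first-day schedule (protocol 7.2; SAP 1.2 and 6.2.5) with the maximum-daily-dose sentence (protocol synopsis; SAP 1.2), and the text of protocol 7.2 with Table 8 on 2-PE days. This review takes no view on which is right. Then replace both overdose sub-lines with one rule: administrations above the number that the reconciled protocol schedules for that subject on that day. State how the i.v. bolus is counted and what a day means. If the reconciled schedule still differs by arm on 2-PE days, the count will need the assignment; square this with SAP 2, which sets exclusions without regard to it.
3. **SAP 2:** delete the completion clause so that PP matches protocol 10.1 and SAP 6.2.2.

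The cost is SAP wording before database lock and one reconciliation of the dosing passages. No new data are needed, and neither N nor the ITT analysis changes.
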